### 7.3.2 Complete Response

The primary endpoint of CR rate will be calculated as the number of subjects with a best response of CR divided by the total number of subjects included in the efficacy analysis. The CR rate will be compared between the 2 treatment groups using a Cochran Mantel-Haenszel test at an alpha level of 0.04 stratified by the stratification factors used at randomization: age (<75 or ≥75 years), ECOG performance status (0-1, 2-3), study center region (North America, Europe, ROW), and secondary AML (secondary to MDS or other antecedent hematologic disorder) or poor-risk cytogenetics (Yes, No/Unknown). The null and alternative hypotheses are:

- **Null hypothesis  $H_0$ :** CR rates are the same between the guadecitabine treatment and TC treatment
- **Alternative hypothesis  $H_1$ :** CR rates are different between the two treatment arms

A 2-sided  $p$  value of  $\leq 0.04$  will be judged as statistically significant. In addition, a normal approximated, two-sided 96% CI for the (Mantel-Haenszel weighted) difference in CR rates between guadecitabine treatment and TC treatment will be provided (Koch et al 1990).

The following sensitivity analyses will be conducted for the co-primary endpoint of CR rate for evaluating robustness of the treatment effect:

- 1) The CR rate will be compared between the guadecitabine and TC using a regular Chi-square test without stratification.
- 2) A logistic regression analysis will be performed for the primary endpoint of CR with treatment group (guadecitabine or TC), age (<75 or ≥75 years old), ECOG performance status (0-1, 2-3), the geographic region (North America, Europe, ROW) of the study centers, and secondary AML or poor-risk cytogenetics (Yes, No/Unknown) as fixed factors. The point estimate and 95% CI, as well as the  $p$  value will be provided for the odds ratio (OR) comparing the odds of being a responder in guadecitabine treatment with the odds of being a responder in TC treatment.
- 3) An "as-treated" analysis will be conducted on the CR rate, based on treatment actually received as described in Section 5.3, using the same Cochran Mantel-Haenszel test and same

stratification variables described above. Subjects who were randomized but not treated will not be included in this analysis.

- 4) The CR rate will be calculated and analyzed using the same Cochran Mantel-Haenszel test and same stratification variables described above with the subjects who were classified as nonevaluable for efficacy (NE subjects) excluded from the Efficacy Analysis Set.
- 5) The CR rate will be calculated and analyzed using the same Cochran Mantel-Haenszel test and stratification variables described above excluding subjects whose AML diagnosis cannot be confirmed by WHO classification by the independent central reader.

### 7.3.3 Overall Survival

For the OS analysis, survival time is defined as the number of days from the day the subject was randomly assigned to study treatment to the date of death (regardless of cause).

$$\text{Survival time in days} = (\text{earliest date of death or censoring} - \text{date of randomization})$$

Survival time will be censored on the last date the subject is known alive with no event of death. OS curves will be estimated using Kaplan-Meier method and formally compared between the two treatment groups using a 2-sided stratified log-rank test, stratified by the same stratification factors used at randomization. The null and alternative hypotheses are:

- **Null hypothesis  $H_0$ :** Survival curves are the same between the two treatment arms
- **Alternative hypothesis  $H_1$ :** Survival curves are different between the two treatment arms

If the CR rate analysis is significant, OS will be tested at an alpha level of 0.05; without a significant CR rate test result, OS will be tested at an alpha level of 0.01, as described in Section 7.3.7. The stratification variables will include age (<75 or  $\geq$ 75 years), ECOG performance status (0-1, 2-3), study center region (North America, Europe, ROW), and secondary AML or poor-risk cytogenetics (Yes, No/Unknown). The median (and quartiles) duration of OS and the associated 95% CI for each treatment arm will be estimated using the Kaplan-Meier method and the  $\log(-\log(\cdot))$  transformation for the survival function. The 12-month survival rate estimate will also be provided for each treatment arm.

In addition, the HR and its 95% CI will be estimated using a Cox proportional-hazard model with treatment group as the independent variable and stratified by the same randomization stratification factors as used for the log-rank test. In a supportive analysis, the assumption of proportional hazards will be evaluated to assist interpretation of the Cox regression analysis results.

The following sensitivity analyses will be conducted for the co-primary endpoint of OS for evaluating robustness of the treatment effect:

- 1) The OS will be analyzed using Kaplan-Meier method and compared between the guadecitabine and TC using log-rank test without stratification.
- 2) An "as-treated" analysis will be conducted for the OS, based on treatment actually received as described in Section 5.3, using the same Kaplan-Meier method and 2-sided stratified log-rank test described above. Subjects who were randomized but not treated will not be included in this analysis.
- 3) This analysis will be conducted using the same Kaplan-Meier method and 2-sided stratified log-rank test described above. However, the survival time will also be censored on the date the subject receives other anti-leukemia treatments, including chemotherapy and hematopoietic cell transplant (HCT), recognizing the fact that this analysis could diminish a true treatment effect since HCT are given to subjects whose disease is well controlled and other anti-leukemia therapies are usually given to subjects at the time of their disease progression.
- 4) This analysis will be conducted using the same Kaplan-Meier method and 2-sided stratified log-rank test described above, excluding subjects whose AML diagnosis cannot be confirmed by WHO classification by the independent central reader.

#### 7.3.4 Composite CR

The CRc rate is calculated as the number of subjects with a best response of CR, CRp, or CRi divided by the total number of subjects included in the efficacy analysis. The CRc rate will be compared between the 2 treatment groups using a Cochran Mantel-Haenszel test with the stratification variables the same as for CR and OS. If CR rate analysis and OS analysis are both significant, the CRc rate will be tested at an alpha level of 0.05; with a nonsignificant CR rate result ( $p > 0.04$ ) and a significant OS result at the 0.01 level, the CRc rate will be tested at an alpha level of 0.01 (see Section 7.3.7). In addition, the 2-sided 95% (or 99%, as appropriate) CI for the Mantel-Haenszel weighted difference in CRc rate between the 2 treatment groups will be provided.

#### 7.3.5 Number of Days Alive and Out of the Hospital

The date of each hospital admission and discharge will be collected for each subject for a minimum 6 months (and until termination of study treatment if the study treatment lasts for more than 6 months), unless the subject dies or withdraws consent prior. The duration of each hospital stay in days (regardless of the reason for hospitalization) is calculated as:

$$\text{Duration} = \text{date of discharge} - \text{date of admission}$$

For a subject who is admitted and discharged on the same day the duration of hospital stay will be 0. The total duration of all hospital stays in the first 6 months is the sum of all individual

durations of hospital stays occurred between C1D1 and Day 180. For ease of calculation, one month is defined as 30 days for analyses conducted in this study. The NDAOH within the first 6 month period is calculated as:

$$\text{NDAOH} = 180 - \text{total duration of all hospital stays} - \text{number of death days before Day 180}$$

The number of death days before Day 180 = (date of Day 180 - date of death, if death occurs before Day 180). For subjects who die on or after Day 180 the number of death days before Day 180 will be set to 0. For subjects who are lost to follow-up within 6 months (expected to be a very small number), the NDAOH will be calculated conservatively assuming that the subject would have died the day after the last contact day.

The NDAOH will be summarized by treatment group and compared between the 2 treatment groups using an analysis of variance model at an alpha level of 0.05 or 0.01 as appropriate, if the CRc test result is significant at that required level (see Section 7.3.7). The variables used for stratification at randomization will be included in the analysis of variance model as fixed factors.

In addition, to utilize the information on hospital stays beyond 6 months, the NDAOH will also be calculated in a similar way to 6 months or the date of treatment discontinuation (whichever occurs later) and summarized as a per patient-year rate for each treatment group.

### 7.3.6 Progression-free Survival

Progression is defined as the earliest occurrence of one of the following:

- For subjects with CR, CRi, or CRp, the confirmed (at least 2 PB samples at least 1 week apart) appearance of leukemic blasts in PB by investigator or central assessment, OR  $\geq 5\%$  leukemic blasts in the BM by blinded central pathologist assessment.
- For all other subjects, when PB or BM shows evidence of continued increase in blasts % that necessitates alternative therapy.
- Death.

PFS is defined as the number of days from randomization to the earliest date of investigator's assessment of disease progression, subject receives an alternative anti-leukemia therapy, or relapse by PB assessment or blinded BM assessment, whichever occurs first, or death (regardless of cause). PFS time will be censored on the last date the subject is known to be alive without a relapse/disease progression.

$$\text{PFS in days} = (\text{earliest date of progression, relapse, alternative anti-leukemia therapy, death or censoring} - \text{date of randomization})$$

PFS will be compared between the 2 treatment groups using a stratified log-rank test (by the same stratification factors as used at randomization) at an alpha level of 0.05, or 0.01, as appropriate, if CRc and NDAOH test results are significant at that required level (see

[figure not shown]
Section 7.3.7). The median (and quartiles) duration of PFS and the associated 95% CI for each treatment arm will be estimated using the Kaplan-Meier method. In addition, the HR and its 95% CI will be estimated using a Cox proportional-hazard model with treatment group as the independent variable and stratified by the same randomization stratification factors as used for the log-rank test. In a supportive analysis, the assumption of proportional hazards will be evaluated to assist interpretation of the Cox regression analysis results.

### 7.3.7 Test Sequence and Procedures of Statistical Tests for Efficacy Endpoints

To control the alpha errors associated with testing the multiple endpoints of CR rate, OS, CRc rate, NDAOH, and PFS, the following test sequence and procedures will be followed, assuming that the study continues after the planned interim analysis.

The primary efficacy variable CR rate will be tested first in the sequence at an alpha level of 0.04. A positive CR analysis ( $p \leq 0.04$ ) serves as a gatekeeper (Westfall and Krishen 2001) for the subsequent analyses. If the test for CR is positive (ie,  $p \leq 0.04$ ), then hierarchical analyses will be conducted at the 0.05 alpha level for the efficacy variables OS, CRc rate, NDAOH, and PFS (in that order). If the test for CR is not significant at the 0.04 level, then hierarchical analyses will be conducted at the 0.01 level for the efficacy variables OS, CRc, NDAOH, and PFS. The hierarchical test order and alpha value to be used for each test at the primary analysis time point are further described in Figure 2.

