## 4.0 SAMPLE SIZE

By trial design, the overall (2-sided) alpha level of 0.05 is split between the co-primary endpoints of CR (0.04) and OS (0.01). A formal interim analysis will be performed only for OS using a group sequential boundary preserving an overall (2-sided) 0.01 alpha level. The sample size calculation for the primary analysis of CR is based on testing at the 0.04 nominal alpha level. If statistical significance is achieved for CR, hierarchically, the final analysis of OS will be conducted to preserve an overall 2-sided 0.05 alpha level, accounting for alpha spent at the interim analysis of OS, as described in Section 11.6.7 and Section 11.9 of the study protocol (see Section 7.3.7 and 7.6). The sample size calculation for OS will be shown for the setting of a 2-sided 0.05 alpha level.

Assuming a CR rate of approximately 0.20 ([Kantarjian et al 2012](#); [Fenaux et al 2010](#); [Burnett et al 2007](#)) for subjects treated in the TC group (all TC therapies combined) and assuming an increase in CR rate to 0.30 or higher can be achieved by treating subjects with guadecitabine,

800 subjects (400 per treatment group) will provide approximately 89% power to detect the overall difference of 0.10 when using a 2-sided Cochran Mantel-Haenszel test having 2-sided alpha level of 0.04. For the purpose of this sample size calculation, the constant CR rates of 0.20 and 0.30 for the TC and guadecitabine groups, respectively, are assumed for each stratum.

For survival, an analysis at 670 death events will provide 90% power to detect a HR of approximately 0.78 (a difference in median survival of 7 months in the TC group versus 9 months in the guadecitabine group), when using a 2-sided stratified log-rank test at an 0.05 alpha level. Accrual is expected to be uniform over a 21 month enrollment period, with an additional follow-up of 12 months. Hence, the assessment of survival needs approximately the same sample size of 800 subjects. Primary response and survival analyses will be performed after 670 death events have occurred. For the purpose of this sample size calculation, a constant HR of approximately 0.78 was assumed for all strata defined by the stratification factors.

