## 7.3 Efficacy Variables and Analyses

Efficacy analyses will be based on the Efficacy Analysis Set, except where it is specified otherwise. This section describes the analyses conducted at the primary analysis time point when 670 death events have occurred, assuming that the study continued after the planned interim analysis. The alpha levels referenced in this section are nominal alpha levels for judging statistical significance, taking into consideration the planned interim analysis and the hierarchical testing order of the (final) primary analysis. The overall experimental alpha error is controlled at the 2-sided 0.05 level.

The co-primary efficacy endpoints are CR rate based on IWG 2003 AML Response Criteria ([Cheson et al 2003](#)) and OS. If either of the co-primary efficacy endpoints reaches statistical

significance in favor of guadecitabine at either the interim analysis (OS only) or final analysis (CR and OS), then the study will be considered positive in efficacy.

Secondary efficacy endpoints include CRc, NDAOH, PFS, number of RBC transfusions, and separately, number of platelet transfusions over the duration of the study treatment, the EQ-5D-5L descriptive system and the EQ VAS, as well as duration of CR.

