## 7.6 Interim Analyses and Data Monitoring

Data will be reviewed by an independent DMC at regular intervals primarily to evaluate safety during study conduct. The committee will operate independently from the Sponsor and the clinical investigators.

One formal interim analysis of OS is planned, providing the DMC a chance to recommend stopping the trial earlier in case the study treatment shows an overwhelming effect on survival. This interim analysis will be conducted by the independent DMC after approximately half (ie, approximately 335) of the required death events have occurred using the same statistical methods as described in Section 7.3. All data available at the time of clinical data cut for the interim analysis will be included in the interim analysis. Inclusion of additional available data beyond the clinical data cut will be at the discretion of DMC. The nominal alpha values for the interim and final OS analyses are based on Lan-DeMets implementation of the O'Brien-Fleming boundary (Lan and DeMets 1983; O'Brien and Fleming 1979). With one interim analysis at 50% information time point plus one final analysis, the 2-sided alpha-boundaries are 0.00014 and 0.00995, respectively.

If the trial continues after the interim analysis, and if the primary analysis of CR rate is significant at the 0.04 level, the alpha level for the primary analysis of OS will be  $0.04 + 0.00995 = 0.04995 \approx 0.05$ . If the trial continues after the interim analysis, and if the primary analysis of CR rate is not significant at the 0.04 level, the alpha value for the primary analysis of OS will be  $0.00995 \approx 0.01$ . The overall alpha error is controlled at the 0.05 level.

In the unlikely scenario of having observed a significant ( $p \leq 0.00014$ ) positive OS result at the planned interim analysis time point with an acceptable safety profile of guadecitabine, the DMC may choose to analyze the co-primary endpoint CR at an appropriate alpha level to be determined by DMC before making a recommendation to the Company. The Company does not intend to announce the interim analysis results and make any decision to prematurely terminate the study, for any reason other than major safety concerns, without discussing the data and recommendation from the DMC first with the major regulatory agencies.

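### The final OS test levels in SAP 7.3.3 and 7.3.7 are rounded up from the boundary derived in SAP 7.6, so the stated OS alpha is very slightly overspent

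*SAP*

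**What the plan says.** SAP 4.0 sets the requirement. The trial's two-sided 0.05 is divided into 0.04 for CR and 0.01 for OS. On the OS share it says: "A formal interim analysis will be performed only for OS using a group sequential boundary preserving an overall (2-sided) 0.01 alpha level". After a CR success, "the final analysis of OS will be conducted to preserve an overall 2-sided 0.05 alpha level, accounting for alpha spent at the interim analysis of" that endpoint.

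SAP 7.6 derives the boundary. The interim comes "after approximately half (ie, approximately 335) of the required death events have occurred", and with Lan-DeMets O'Brien-Fleming spending "the 2-sided alpha-boundaries are 0.00014 and 0.00995, respectively". It then gives the final OS level as 0.04 + 0.00995 = 0.04995 if CR succeeds, written as approximately 0.05, and as 0.00995 if CR fails, written as approximately 0.01.

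SAP 7.3.3 and 7.3.7 use only the rounded figures. Section 7.3.3 has: "If the CR rate analysis is significant, OS will be tested at an alpha level of 0.05", and 0.01 otherwise. Section 7.3.7 repeats this in the testing sequence: "If the test for CR is not significant at the 0.04 level, then hierarchical analyses will be conducted at the 0.01 level". The introduction to 7.3 gives these figures their status: "The alpha levels referenced in this section are nominal alpha levels for judging statistical significance, taking into consideration the planned interim analysis".

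Protocol 11.6.3, 11.6.7 and 11.9 carry the same figures. Section 7.3.7 refers to Figure 2 for the alpha values, but the figure is not shown in the text available to me.

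**The concern.** If the 7.3 levels are nominal and net of the interim, they should equal the final boundary in 7.6. They do not: 0.01 and 0.05 are the full OS allotments before anything is deducted for the interim. In the CR-fails branch, the rounding removes the whole adjustment that the boundary was calculated to make.

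OS is a co-primary endpoint, and success on either co-primary makes the study positive. For a final OS p value between 0.00995 and 0.01 (CR not significant), or between 0.04995 and 0.05 (CR significant), the call depends on whether the computed or the rounded figure decides. No sentence settles that explicitly, and it is better settled before the result is known.

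**Working it through.** **Inputs.** OS alpha 0.01 two-sided, or 0.05 in total after a CR success (SAP 4.0). Interim at about 335 of 670 deaths, so information fraction t = 0.5. Lan-DeMets O'Brien-Fleming spending, interim level 0.00014, final level 0.00995 (SAP 7.6).

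**Step 1: reproduce the plan's boundaries.** With 0.005 per side, the spend per side at fraction t is 2[1 − Φ(z / √t)], where z is the 1 − 0.0025 normal quantile, 2.807.
- At t = 0.5: 2.807 / √0.5 = 3.970 and 1 − Φ(3.970) = 0.0000360. The spend is 0.000072 per side, or 0.000144 two-sided, so the interim critical value is c1 = 3.801.
- The final critical value c2 solves P(|Z1| ≥ c1 or |Z2| ≥ c2) = 0.01, with (Z1, Z2) bivariate normal and correlation √0.5. The solution is c2 = 2.578, nominal p = 0.00995.

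Both of the plan's figures are reproduced.

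**Step 2: total OS type I error for each final level**, using the same probability with c1 = 3.801:

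| Final OS level | Total OS error | Limit |
|---|---|---|
| 0.00995 (CR fails, computed) | 0.010001 | 0.01 |
| 0.01 (CR fails, rounded) | 0.010051 | 0.01 |
| 0.04995 (CR succeeds, computed) | 0.049966 | 0.05 |
| 0.05 (CR succeeds, rounded) | 0.050016 | 0.05 |

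The 0.010001 in the first row is itself a rounding artefact: with the interim level at the printed 0.00014 the total is 0.009999. The excess from rounding up is about 0.00005 in the first branch and 0.00002 in the second.

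**Step 3: effect on the decision.** The critical hazard ratio at 670 deaths is approximately exp(−2c2 / √670).
- 0.01 against 0.00995: 0.8195 against 0.8194.
- 0.05 against 0.04995: 0.85947 against 0.85944.
- Power at HR 0.78: 0.7388 against 0.7383, and 0.895 at both of the higher levels.

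**Step 4: if the interim is not at exactly 50%.** The interim boundary is recomputed from the spending function at each fraction. The third and fourth columns give total OS error with the final level held fixed. The last column gives the final level that restores 0.01.

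| Fraction (deaths) | Interim level | Total, final 0.01 | Total, final 0.00995 | Final level needed |
|---|---|---|---|---|
| 50% (335) | 0.00014 | 0.010051 | 0.010001 | 0.00995 |
| 55% (369) | 0.00031 | 0.010105 | 0.010056 | 0.00989 |
| 60% (402) | 0.00058 | 0.010194 | 0.010144 | 0.00980 |

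Hard-coding 0.00995 therefore does not hold 0.01 if the look is late. At 55% it overspends by 0.000056, slightly more than the rounding itself does at 50%.

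**The case against.** A reader might infer that the SAP contains two rival rules for one test, so that the same p value wins under 7.3.7 and loses under 7.6. The documents do not support that. Section 7.6 puts both sets in a single chain of arithmetic with an approximation sign, SAP 4.0 refers to 7.3.7 and 7.6 together, and the protocol does the same. This is one boundary written at two precisions.

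A reader might also infer that the claim of overall control at 0.05 fails materially. It does not:
- With both nulls true, and CR and OS assumed independent, the family-wise rate with the rounded level is 0.04 + 0.96 × 0.010049 = 0.0496.
- With only OS null and CR at its planned 89% power, again assuming independence, it is 0.89 × 0.050015 + 0.11 × 0.010049 = 0.0456.
- It exceeds 0.05 only at the additive bound (0.04 + 0.010049 = 0.050049) or as CR power approaches 1 (0.050015).

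(These three use the printed interim level of 0.00014.)

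Finally, the log-rank test is itself a normal approximation with up to 2 × 2 × 3 × 2 = 24 strata, so fifth-decimal exactness has limited meaning.

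All of this stands as to size. It does not remove the point: the rounding goes in the anti-conservative direction, SAP 7.3 describes the rounded levels as already net of the interim when they are not, and an approximation sign is not a decision rule.

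**Conclusion.** The point holds as disclosed but anti-conservative rounding of a co-primary threshold. With the interim at 50% information, total OS error is about 0.01005 against 0.01, or 0.05002 against 0.05. The effect on power and on the critical hazard ratio is negligible, and only a final OS p value in one of two bands, each 0.00005 wide, would be affected. It concerns the OS step alone, because CRc, NDAOH and PFS have no planned formal interim test.

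The figures rest on symmetric two-sided spending, which reproduces the plan's boundaries, and on the usual joint normal approximation for the two log-rank statistics. Nothing is concluded about Figure 2, whose content I have not seen. This is a minor, editorial-level correction.

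**What to change.** In SAP 7.3.3 and 7.3.7 (and protocol 11.6.3 and 11.6.7), refer the final OS level to the boundary in SAP 7.6 (protocol 11.9): 0.00995 if CR fails and 0.04995 if CR succeeds, when the interim is at exactly 50% information. Amend Figure 2 only if it prints the rounded values. Delete the roundings to 0.01 and 0.05 in 7.6 and 11.9.

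Add a sentence that the final OS level will be recalculated from the Lan-DeMets spending function at the actual interim and final event counts. For an interim at 55%, this gives about 0.00989 in the CR-fails branch. Keeping the plan's own addition, the CR-succeeds level is then 0.04 + 0.00989 = 0.04989. That sum is slightly conservative: at 50% information about 0.04998 would be admissible, against the plan's 0.04995.

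The cost is a wording edit. Sample size, event target and interim timing do not change, and at 50% information the power lost is about 0.0006 (0.7388 to 0.7383) in the CR-fails branch and less in the other.
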